8.1. Immunogenicity Assessments

8.1.1. Immunogenicity Assessments

Venous blood samples will be collected for assessment of humoral immune responses and cellular immunogenicity (RNA sequencing) in all participants. Blood for evaluation of humoral and cellular (PBMC in subset only) immune responses will be drawn from participants at the time points specified in the Schedule of Activities. Cellular immune responses (PBMC) will only be

assessed in a subset of adult participants in Groups 1-6 (approximately 112; 21 participants per group in Groups 1-5, 7 participants in Group 6; at selected sites) Immunogenicity assessments may include, but are not limited to, the humoral and cellular immunogenicity assays (as available and feasible) summarized in the below table. Sample volumes and time points are detailed in the Schedules of Activities in Section 1.3.

If the participant is unable to complete the study without withdrawing consent/assent, immunogenicity samples will be taken at the early exit visit, but only if the early exit visit is at least 10 days after the previous immunology blood draw. See Section 1.3, Schedule of Activities for further details.

Humoral and cellular immunogenicity assays may include, but are not limited to, the assays summarized in Table 8.

Table 8: Summary of Humoral and Cellular Immunogenicity Assays

•	air and Centrial Immunogementy Assays			
Assay Purpose				
Humoral Immunogenicity				
Primary/Secondary/Exploratory				
endpoints				
SARS-CoV-2 neutralization	Analysis of neutralizing antibodies to the wild-type virus and/or			
(VNA)	pseudovirion expressing S protein			
SARS-CoV-2 binding antibodies	Analysis of antibodies binding to SARS-CoV-2 or individual SARS-CoV-2			
(ELISA)	proteins (eg, S protein)			
Exploratory endpoints				
SARS-CoV-2 binding antibodies	Analysis of antibodies binding to the SARS-CoV-2 N protein, if such an			
(ELISA)	assay is available			
SARS-CoV-2 binding antibodies	Analysis of antibodies binding to the SARS-CoV-2 S protein (different than			
(MSD)	the assays supportive of the secondary objectives) and the RBD of the			
	SARS-CoV-2 S protein			
Functional and molecular antibody	Analysis of antibody characteristics including Fc-mediated viral clearance,			
characterization	avidity, Fc characteristics, Ig subclass and IgG isotype			
Passive transfer	Analysis of immune mediators correlating with protection against			
	experimental SARS-CoV-2 challenge in a suitable animal model			
SARS-CoV-2 neutralizing	Analysis of neutralizing antibodies against emerging SARS-CoV-2 variants			
antibodies				
Adenovirus neutralization	Analysis of neutralizing antibodies to adenovirus			
(neutralization assays)	θ			
Cellular Immunogenicity	I			
Exploratory endpoint				
Flow cytometry (ICS)	Analysis of T-cell responses to SARS-CoV-2 S protein, and/or other protein			
,	peptides by ICS including CD4 ⁺ /CD8 ⁺ , IFNy, IL-2, TNF α , IL-4, IL-5,			
	IL-13, and/or other Th1/Th2 markers			
Gene expression analysis	Analysis of gene expression by RNA transcript profiling			

CD = cluster of differentiation; ELISA = enzyme-linked immunosorbent assay; IFN γ = interferon gamma; IL = interleukin; MSD = meso scale discovery; PBMC = peripheral blood mononuclear cell; RBD = receptor-binding domain; RNA = ribonucleic acid; S = Spike protein; SARS-CoV-2 = severe acute respiratory syndrome coronavirus-2; Th = T helper; TNF α = tumor necrosis factor alpha; VNA = virus neutralization assay

8.1.2. Procedures in Case of (Suspected) COVID-19

Participants will be provided with a booklet including a daily question on whether they are experiencing COVID-19-like symptoms, and for documentation of body temperature and pulse oximetry results. Baseline pulse oximetry will be conducted at Visit 1. During the study, study-site personnel will remind participants to complete the SIC in the event of any signs and symptoms and to contact the site at the time of symptom onset or in case of a positive RT-PCR test for SARS-CoV-2 (regardless of where the testing was performed). This positive RT-PCR test will need to be captured in the eCRF.

If a participant meets one of the prespecified criteria for (suspected) COVID-19²² (see Section 8.1.2.1), the following should take place (for details, see the Schedule of Activities in Section 1.3.7):

- Participants should contact the study site at the time of symptom onset/at time of becoming aware of the positive RT-PCR test.
- If the trigger was a sign or symptom: a nasal swab should be collected by the participant at home (using available material for home swabs) or at the study site as soon as possible and preferably no longer than 2 to 3 days after the onset of symptoms, and stored appropriately. It is preferred that the swab is taken by a caregiver (spouse, partner, relative, friend, or health care professional). If that is not possible, the participant can collect the swab himself or herself. The nasal swab sample collection and storage instructions will be described separately. The site should arrange transfer of the sample to the study site as soon as possible after sample collection. If the trigger was a positive RT-PCR test, then this first nasal swab is not needed.
- A second nasal swab will be obtained on COVID-19 Day 3-8 following the same procedures as the first nasal swab. The second nasal swab may also be collected at home, at the hospital, or at another location, if needed, by a study site staff, if appropriate procedures are in place. The presence of SARS-CoV-2 infection will be assessed at the study site by molecular testing using the nasal swab samples. The nasal swabs may be tested at the central laboratory for the presence of SARS-CoV-2 and other respiratory pathogens using a broad respiratory pathogens panel. Leftover nasal swab samples will be stored and might be used for central laboratory confirmation and/or quantification of SARS-CoV-2 and for detection of other respiratory pathogens. A physical examination, vital signs measurements and pulse oximetry will be performed and a blood sample for assessment of the humoral immune response and other biomarkers will be taken.
- From COVID-19 Day 3-8 onwards: Additional swabs should be taken by a healthcare professional from the participant as soon as possible, but with a minimum of 1 day between the swabs, until 2 consecutive negative swabs are obtained, ie, twice weekly or more frequently until resolution. These precautionary measures are to ensure that site staff who

²² As several of the prespecified criteria for suspected COVID-19 overlap with vaccine-related reactogenicity, investigators' clinical judgement is required to exclude vaccine-related events.

come into physical contact with a participant deemed to be a COVID-19 case undertake the proper safety procedures such as wearing of personal protective equipment.

- Participants should complete the SIC (see Section 10.7) and record their highest body temperature daily starting on the first day of trigger onset. Blood oxygen saturation and pulse rate should be measured using a pulse oximeter 3 times a day, preferably in the morning, at lunch time, and in the evening.
- Collection of data will continue until resolution of the COVID-19 episode, defined as having 2 consecutive days with no COVID-19-related signs or symptoms and 2 consecutive SARS-CoV-2 negative nasal swabs.

8.1.2.1. Prespecified Criteria for (Suspected) COVID-19

The criteria for (suspected) COVID-19 (ie, the triggers to start procedures explained in Section 8.1.2) are prespecified as follows:

-

²³ The study staff visiting participants at home will use personal protective equipment according to local regulations.

Positive RT-PCR result for SARS-CoV-2, regardless where the testing was performed (under the auspices of the study or through a private or public laboratory independent of the study), whether symptomatic or asymptomatic

OR

New onset or worsening of any 1 of these symptoms, which lasts for at least 24 hours, not otherwise explained:

- Headache
- Malaise (appetite loss, generally unwell, fatigue, physical weakness)
- Myalgia (muscle pain)
- Chest congestion
- Cough
- Runny nose
- Shortness of breath or difficulty breathing (resting or on exertion)
- Sore throat
- Wheezing
- Eye irritation or discharge
- Chills
- Fever ($\ge 38.0^{\circ}$ C or $\ge 100.4^{\circ}$ F)
- Pulse oximetry value $\leq 95\%$, which is a decrease from baseline
- Heart rate ≥90 beats/minute at rest, which is an increase from baseline
- Gastrointestinal symptoms (diarrhea, vomiting, nausea, abdominal pain)
- Neurologic symptoms (numbness, difficulty forming or understanding speech)
- Red or bruised looking toes
- Skin rash
- New or changing olfactory or taste disorders
- Symptoms of blood clots: pain/cramping, swelling or redness in your legs/calves
- Confusion
- Bluish lips or face
- Clinical suspicion/judgment by investigator of symptoms suggestive of COVID-19, including MIS-C (multisystem inflammatory syndrome in children [adolescent participants only])

As several of the prespecified criteria for suspected COVID-19 overlap with vaccine-related reactogenicity, investigators' clinical judgment is required to exclude vaccine-related events.

8.2. Safety Assessments

Details regarding the SMC are provided in Section 10.3.6.

AEs will be reported and followed by the investigator as specified in Section 8.3 and Section 10.4.

Any clinically relevant changes occurring during the study must be recorded on the AE section of the eCRF.

Any clinically significant abnormalities persisting at the end of the study/early withdrawal will be followed by the investigator until resolution or until a clinically stable condition is reached.

The study will include the following evaluations of safety and reactogenicity according to the time points provided in the Schedule of Activities (Section 1.3).

8.2.1. Physical Examinations

A history-directed physical examination, including height and body weight, will be carried out at screening. To obtain the actual body weight, participants must be weighed lightly clothed. The height should be measured without footwear.

At all other visits, an abbreviated, symptom-directed examination might be performed by the investigator based on any clinically relevant issues or symptoms, and medical history. Symptom-directed physical examination may be repeated if deemed necessary by the investigator.

Physical examinations will be performed by the investigator or designated medically trained clinician. Any clinically relevant abnormalities or changes in severity observed during the review of body systems should be documented in the eCRF.

8.2.2. Vital Signs

Body temperature (oral route preferred, or in accordance with the local standard of care), pulse/heart rate, respiratory rate, and blood pressure will be assessed.

Participants will utilize a diary to record body temperature measurements post-vaccination.

Blood pressure and pulse/heart rate measurements will be assessed supine with a completely automated device. Manual techniques will be used only if an automated device is not available.

Blood pressure and pulse/heart rate measurements should be preceded by at least 5 minutes of rest in a quiet setting without distractions (eg, television, cell phones). Vital signs are recommended before blood sampling.

8.2.3. Pregnancy Testing

A urine pregnancy test for women of childbearing potential will be performed at screening and before each vaccination.

Additional pregnancy tests may be performed, as determined necessary by the investigator or required by local regulation, to establish the absence of pregnancy at any time during the participation in the study.

For an adolescent participant who becomes pregnant, this information will be shared with the study participant's legal guardian as required or permitted by local regulations.

8.2.4. Hematology Clinical Laboratory Assessments

Blood samples for hematology (as detailed in Section 10.2) to evaluate D-dimers and Lupus anticoagulant, anti- β 2 glycoprotein, anti-cardiolipin (adults) and anti-PF4 (adults and adolescents) will be collected at the timepoints indicated in the Schedules of Activities (see Section 1.3). For timepoints that have already passed before protocol Amendment 2 was approved and implemented, the D-dimers, Lupus anticoagulant, and anti-PF4 tests will not be performed retrospectively, as these tests are to be performed in plasma samples. Serum samples originally drawn or yet to be drawn for the humoral immunogenicity assessments will be used for the testing of Anti- β 2 glycoprotein, anti-PF4 and anti-cardiolipin. Collection of plasma and serum samples for testing of D-dimers, Lupus anticoagulant, Anti- β 2 glycoprotein, anti-PF4, and Anti-cardiolipin will be performed for all groups from the time of approval of Amendment 3.

The investigator must review the laboratory results, document this review, and record any clinically relevant changes occurring during the study in the AE or medical history section of the case report form (CRF), as applicable.

In case of a thrombotic event or TTS, every effort should be made to collect local hospital/laboratory test results obtained by the treating physician to allow rapid diagnosis and treatment. This information should be reported through the TTS AESI form (see Section 10.13, Appendix 13) electronically per instructions in the eCRF completion guidelines. In addition, every

effort should be made to collect blood samples from the participant for a platelet count (local laboratory or substitute for local laboratory) and other applicable testing (central laboratory) (see the Schedule of Activities in Section 1.3.8 and Section 10.2, Appendix 2). The Investigator will review the laboratory test results to assist the investigation of the AESI.

See Section 8.3.6.1 for details on laboratory test details to be reported for an AE of thrombocytopenia.

8.3. Adverse Events, Serious Adverse Events, Adverse Events of Special Interest, and Other Safety Reporting

Timely, accurate, and complete reporting and analysis of safety information, including AEs, suspected AESIs, SAEs, and product quality complaint (PQC), from clinical studies are crucial for the protection of participants, investigators, and the sponsor, and are mandated by regulatory agencies worldwide. The sponsor has established Standard Operating Procedures in conformity with regulatory requirements worldwide to ensure appropriate reporting of safety information; all clinical studies conducted by the sponsor or its affiliates will be conducted in accordance with those procedures.

AEs will be reported by the participant (or, when appropriate, by a caregiver, surrogate, or the participant's legally acceptable representative) for the duration of the study.

Further details on AEs, suspected AESIs, SAEs, and PQC can be found in Section 10.4.

8.3.1. Time Period and Frequency for Collecting Adverse Event, Adverse Event of Special Interest, and Serious Adverse Event Information

All Adverse Events

AEs and special reporting situations, whether serious or non-serious, that are related to study procedures or that are related to non-investigational sponsor products will be reported for all participants from the time a signed and dated ICF is obtained until the end of the study/early withdrawal.

Clinically relevant medical events not meeting the above criteria and occurring between signing of the ICF and moment of first vaccination will be collected on the Medical History eCRF page as pre-existing conditions.

Solicited AEs, collected through a diary, will be recorded for each vaccination from the time of vaccination until 7 days post-vaccination.

All other unsolicited AEs and special reporting situations, whether serious or non-serious, will be reported for each vaccination from the time of vaccination until 28 days post-vaccination. Unsolicited AEs with the onset date outside the timeframe defined above (>28 days after previous study vaccination), which are ongoing on the day of the subsequent vaccination, should be recorded as such.

All SAEs and AEs leading to discontinuation from the study/vaccination (regardless of the causal relationship) are to be reported for all participants from the moment of first vaccination until completion of the participant's last study-related procedure, which may include contact for safety follow-up. The sponsor will evaluate any safety information that is spontaneously reported by an investigator beyond the time frame specified in the protocol.

All AEs will be followed until resolution or until clinically stable.

Adverse Events of Special Interest

From the time of local approval of protocol Amendment 5 onwards, TTS is considered to be an AESI. Suspected AESIs (thrombotic events and thrombocytopenia [defined as platelet count below $150,000/\mu L^0$]) will be recorded from the moment of vaccination until the end of the study/early withdrawal. An AESI Adjudication Committee with appropriate expertise will be established to evaluate each suspected AESI and determine whether it is a case of TTS. (see Section 8.3.6).

Serious Adverse Events

All SAEs, as well as PQC, occurring during the study must be reported to the appropriate sponsor contact person by study-site personnel within 24 hours of their knowledge of the event.

SAEs, including those spontaneously reported to the investigator, must be reported using an SAE form. The sponsor will evaluate any safety information that is spontaneously reported by an investigator beyond the time frame specified in the protocol.

Information regarding SAEs will be transmitted to the sponsor using the Serious Adverse Event Form and Safety Report Form of the CRF, which must be completed and reviewed by a physician from the study site and transmitted to the sponsor within 24 hours. The initial and follow-up reports of an SAE should be transmitted electronically or by facsimile (fax). Telephone reporting should be the exception and the reporter should be asked to complete the appropriate form(s) first.

Adolescents

Signs and symptoms of Multisystem Inflammatory Syndrome in Children (MIS-C) will be monitored and reported as SAE in children with (suspected) COVID-19 as confirmed by a positive RT-PCR result for SARS-CoV-2, and in children of mothers or close relatives with prior (within 4-weeks) or current suspected or confirmed COVID-19. Further details on case definition and reporting of MIS-C in children can be found in section 10.12.

8.3.2. Method of Detecting Adverse Events, Adverse Events of Special Interest, and Serious Adverse Events

Care will be taken not to introduce bias when detecting AEs, suspected AESIs, or SAEs. Openended and nonleading verbal questioning of the participant is the preferred method to inquire about AE occurrence.

Solicited Adverse Events

Solicited AEs are used to assess the reactogenicity of the study vaccine and are predefined local (at the injection site) and systemic events for which the participant is specifically questioned and which are noted by participants in their diary.

After each vaccination, participants will remain under observation at the study site for at least 1 hour for the presence of any acute reactions and solicited events.

In addition, participants (or parents/legal guardians of the minor participants) will record solicited signs and symptoms in a diary for 7 days post-vaccination. All participants will be provided with a diary and instructions on how to complete the diary (see Overview in Section 8, Study Assessments and Procedures). Diary information will be transferred to the sponsor. After review and verbal discussion of the initial diary entries with the participant, the investigator will complete his/her own assessment in the relevant sections of the eCRF. Once a solicited sign or symptom from a diary is considered to be of severity Grade 1 or above, it will be recorded as a solicited AE.

Solicited Injection Site (Local) Adverse Events

Participants will be asked to note in the diary occurrences of injection site pain/tenderness, erythema and swelling at the study vaccine injection site daily for days post-vaccination (day of vaccination and the subsequent 7 days). The extent (largest diameter) of any erythema and swelling should be measured (using the ruler supplied) and recorded daily. The case definitions for solicited injection site events can be found in the references.^{0,0}

Solicited Systemic Adverse Events

Participants will be instructed on how to record daily temperature using a thermometer provided for home use. Participants should record the temperature in the diary in the evening of the day of vaccination, and then daily for the next 7 days approximately at the same time each day. If more than one measurement is made on any given day, the highest temperature of that day will be used in the eCRF.

Fever is defined as endogenous elevation of body temperature ≥38° C, as recorded in at least one measurement.⁰

After each vaccination, participants will remain under observation at the study site for at least 1 hour to monitor for the presence of any acute reactions and solicited events.

Participants will also be instructed on how to note signs and symptoms in the diary on a daily basis for 7 days post-vaccination (day of vaccination and the subsequent 7 days), for the following events: fatigue, headache, nausea, and myalgia.

Unsolicited Adverse Events

Unsolicited AEs are all AEs for which the participant is not specifically questioned in the participant diary.

For details about AESIs, refer to Section 8.3.6.

8.3.3. Follow-up of Adverse Events, Adverse Events of Special Interest, and Serious Adverse Events

The investigator is obligated to perform or arrange for the conduct of supplemental measurements and evaluations as medically indicated to elucidate the nature and causality of the AE, suspected AESI, SAE, or PQC as fully as possible. This may include additional laboratory tests or investigations, histopathological examinations, or consultation with other health care professionals.

AEs, including pregnancy, will be followed by the investigator as specified in Section 10.4.

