1.3. Schedule of Activities (SoA)

Status: Approved, Date: 21 July 2021

1.3.1. Groups 1 to 6 (56-day interval schedule [2-dose and single dose regimens]) – Adults\$

Phase	Screeninga		Study Period													
Clinic Visit #	1	2	3	4	5	6	7	8	9	10	11	12	UB**	13	14	Exit ^b
Visit Timing		Vac 1	Vac 1 + 7 d	Vac 1 + 14 d	Vac 1 + 28 d	Vac 2	Vac 2 + 7 d	Vac 2 + 14 d	Vac 2 + 28 d	Vac 2 + 4 mo	Inj 3 + 7 d	Inj 3 + 28 d		Inj 3 + 6 mo	Vac 2 + 12 mo	
Visit Day ±Window	-28 to 1	1	8±2°	15±3	29±3	57 -3/+7	64*±2°	71*±3	85*±3	169*±14	176*±2°	197*±3		337*±21	393*±21	
Visit Type	Screening	Vaccine 1	Safety		Safety and Immuno	Vaccine 2		Safety and Immuno		Antigen presentation or Placebo Injection 3 ^d	1.1	Safety and Immuno	Unblind to primary vaccination regimen ^t	Safety Phone Call	Safety and Immuno	Early Exit
Written informed consente	•												•			
Inclusion/exclusion criteria	•	•1														
Demographics	•															
Medical history/prestudy meds	•															
Physical examination ^f	•															
Pulse oximetry		●1														
Distribution of pulse oximeter ^g		•														
Vital signs ^h incl. body temperature	•	●2	•	•	•	● ²	•	•	•	●2	•	•			•	●4
Nasal swab sample and test for SARS CoV 2 RNA	●6	●7														
Serological test for anti SARS CoV 2 antibody	●6 8	• ⁷ (8)														
Randomization		●1														
Unblinding													•			
Prevaccination check ⁱ		●1				●1				●1						
Urine pregnancy test	•	●1				●1				●1						
Hematology blood sample plasma, mL ^v						● ¹ 5	●5	●5	●5						●5	
Hematology blood sample serum ^u		□8		□8	□8	□8	□8	□8	□8	□8	□8	□8			□8	

Phase	Screening ^a		Study Period													
Clinic Visit #	1	2	3	4	5	6	7	8	9	10	11	12	UB**	13	14	Exit ^b
Visit Timing		Vac 1	Vac 1 + 7 d	Vac 1 + 14 d	Vac 1 + 28 d	Vac 2	Vac 2 + 7 d	Vac 2 + 14 d	Vac 2 + 28 d	Vac 2 + 4 mo	Inj 3 + 7 d	Inj 3 + 28 d		Inj 3 + 6 mo	Vac 2 + 12 mo	
Visit Day ±Window	-28 to 1	1	8±2°	15±3	29±3	57 -3/+7	64*±2°	71*±3	85*±3	169*±14	176*±2°	197*±3		337*±21	393*±21	
Humoral immunity (serum), blood draw, mL		●¹ 15		• 10	• 10	●¹ 10	• 10	• 10	• 10	●¹ 10	• 10	• 15			• 15	● ³ 10
Cellular immunity (PBMC), blood draw, mL ^k		●¹ 60			• 60				● 60			● 60			● 60	● ³ 60
Cellular immunity (whole blood, PAXgene® tubes), mL		●¹ 2.5														
Vaccination		•				•				•						
1 hour post vaccination observation ¹		•				•				•						
Solicited AE recording		- Conti	- Continuous - Continuous-													

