Unsolicited AE recording ^m		- C	- Continuous through +28 d Continuous through +28 d Continuous through +28 d-													
SAE/AESI recording ⁿ								Coi	ntinuous							•
Concomitant medso								Coi	ntinuous							•
Participant diary distribution ^p		•				•				•						
Participant diary review ^q			•				•				•					
COVID 19 like Symptom surveillance booklet and nasal swab kit training and distribution		•														
(Suspected) COVID 19 surveillance ^r								Con	ntinuous							
Approx. blood draw per day, mL: for participants in the PBMC subset. [for participants not in the PBMC subset]	8 [8]	77.5° [17.5]°		10 [10]	70 [10]	15 [15]	15 [15]	15 [15]	75 [15]	10 [10]	10 [10]	75 [15]			80 [15]	70 [10]
Approx. cumulative blood draw, mL: for participants in the PBMC subset. [for participants not in the PBMC subset]	8 [8]	85.5 ^s [25.5 ^s]		95.5 [35.5]	165.5 [45.5]	180.5 [60.5]	195.5 [75.5]	210.5 [90.5]	285.5 [105.5]	295.5 [115.5]	305.5 [125.5]	385.5 [140.5]			460.5 [155.5]	

- •¹ pre vaccination; •² pre and post vaccination; •³ blood samples for immunogenicity will only be taken if the early exit visit is at least 10 days after the previous immunogenicity blood draw; •⁴ if within 7 days of the previous vaccination; •⁵ if within 28 days of the last vaccination; •⁶ Screening diagnostic test for SARS CoV 2 past or current infection will be performed.
 •⁻ to be repeated pre vaccination if the screening test was done more than 4 days before Day 1. □⁵ No extra blood required. The anti β₂ glycoprotein, anti PF4, and anti cardiolipin tests will be performed retrospectively or prospectively with blood from samples collected for the humoral immunogenicity assessment.
- SAs soon as Group 6 (placebo) participants are unblinded they should follow the procedures as outlined in the Schedule of Activities Section 1.3.4.
- *The timings of visits after the second or third (ie, antigen presentation) vaccination will be determined relative to the actual day of that vaccination.
- **Upon implementation of Amendment 5.
- a. Screening will be performed within 28 days prior to the first study vaccination or on the day of vaccination. If screening is performed on the day of vaccination, Visit 1 and Visit 2 will coincide on Day 1. Screening must be completed and all eligibility criteria must be fulfilled prior to randomization and vaccination.

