- o. Concomitant therapies such as analgesic/antipyretic medications and non-steroidal anti-inflammatory drugs, corticosteroids, antihistamines, and vaccinations must be recorded from the first dose of study vaccine until 28 days after administration of study vaccine, and thereafter, pre-dose on the day of vaccination and for 28 days after the subsequent dose of study vaccine. All other concomitant therapies should also be recorded if administered in conjunction with a confirmed COVID-19 case or with new or worsening AEs reported per protocol requirements outlined in Section 8.3.1.
- p. At Visit 2, in addition to the diary, a ruler and thermometer will be distributed to each participant.
- q. If an event is still ongoing on Day 8, Day 64, or Day 176 the participant should keep the diary after the review and collect information until resolution. The diary should be reviewed again at the next visit.
- r. If a participant meets the prespecified criteria for (suspected) COVID-19 (see Section 8.1.2.1), refer to Section 1.3.7.
- s. In case the screening serological test was done more than 4 days before Day 1 an additional 8 mL of blood will need to be taken (repeat of pre-vaccination test).
- t. With the implementation of protocol Amendment 5, all adult participants will be unblinded, and participants who received placebo (Group 6) will start following the Schedule of Activities for the active vaccine regimen in Section 1.3.4.
- u. Once protocol Amendment 4/5 is approved and implemented, hematology serum samples will be collected for all participants (see Section 10.2, Appendix 2).
- v. Hematology plasma samples to be collected up to protocol Amendment 2.

AE = adverse event; AESI = adverse event of special interest; COVID-19 = coronavirus disease-2019; d = day(s); ICF = informed consent form; meds = medication; mo = months; PBMC = peripheral blood mononuclear cell; SAE = serious adverse event; SARS-CoV-2 = severe acute respiratory syndrome coronavirus-2; UB = unblinding visit; vac = vaccination; vp = virus particles.

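### Section 8.2.4 and the adult schedules contradict each other on whether stored serum is tested for anti-PF4 before and after dose 1, and on when plasma is collected

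*Protocol*

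**What the plan says.** **Anti-PF4.** Protocol Section 8.2.4 rules that, for timepoints passed before Amendment 2 was implemented, "the D-dimers, Lupus anticoagulant, and anti-PF4 tests will not be performed retrospectively, as these tests are to be performed in plasma samples". The next sentence reads "Serum samples originally drawn or yet to be drawn for the humoral immunogenicity assessments will be used for the testing of" three named tests, one of which is anti-PF4. The symbol key to SoA 1.3.1 agrees with that second sentence: "anti PF4, and anti cardiolipin tests will be performed retrospectively or prospectively with blood from samples collected for the humoral immunogenicity assessment". The row "Hematology blood sample serum" carries this symbol at Days 1, 15 and 29 and at every later scheduled blood visit. The row "Hematology blood sample plasma, mL" has entries only at Visits 6, 7, 8, 9 and 14.

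**Plasma period.** Footnote v of SoA 1.3.1 and footnote u of 1.3.2 and 1.3.3 state: "Hematology plasma samples to be collected up to protocol Amendment 2". Section 8.2.4 says that plasma and serum collection "will be performed for all groups from the time of approval of Amendment 3".

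**Serum start.** Section 8.2.4 gives Amendment 3. Footnote u of 1.3.1 and footnote t of 1.3.2 and 1.3.3 give Amendment 4/5.

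**Analysis.** Section 3 lists lupus anticoagulants, D-dimers, anti-PF4 and the related antibodies as exploratory endpoints in adults. SAP 5.1.1 defines baseline as the last assessment before the first vaccination. SAP 5.6.2 tabulates change from baseline and treats every abnormality as emerging when baseline is missing.

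**The concern.** A laboratory reading 8.2.4 cannot tell whether to pull the stored Day 1, 15 and 29 serum for anti-PF4. One sentence forbids it and the next provides for it. The early samples matter most for interpretation. Section 2.3.1 places TTS about one to two weeks after vaccination, and in Groups 1-6 Day 15 is the post-dose-1 blood sample closest to that window.

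If baseline is not tested, someone who was anti-PF4 positive before vaccination cannot be told apart from someone who became positive afterwards. The SAP convention would then put both in the emerging column.

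For D-dimer and lupus anticoagulant, which need plasma, the two stated collection periods do not overlap. A site cannot tell from the protocol whether the plasma draws still printed in its schedule are to be taken.

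**Working it through.** **1. Anti-PF4: the three statements side by side**

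| Source | Matrix | Retrospective testing |
|---|---|---|
| 8.2.4, first statement | plasma | no, for timepoints before Amendment 2 |
| 8.2.4, next sentence | humoral serum, already drawn or still to be drawn | yes, by implication |
| SoA 1.3.1 key | humoral serum | yes, stated |

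The first statement cannot be rescued by using plasma for the early visits, because the plasma row is empty at Days 1, 15 and 29. Under that statement the anti-PF4 results for early visits before Amendment 2 do not exist. Under the other two they do.

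Number affected: planned enrolment in Groups 1-6 is 5 × 75 + 25 = 400, including 25 placebo recipients. This is a ceiling. The documents do not say how many had passed Day 1, 15 or 29 by Amendment 2.

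**2. Plasma period: can the footnote fit the schedule?**

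Appendix 15 dates Amendment 2 at 29 October 2020 and Amendment 3 at 22 December 2020. Collection up to the first and collection from the second share no day.

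The 12-month plasma draw in Groups 1-6 is on Day 393 ± 21, so at the earliest Day 372, which is 371 days after Vaccination 1. For that to fall on or before 29 October 2020, Vaccination 1 would have to be no later than 24 October 2019. Section 2 dates the first reports of the disease to December 2019. The footnote therefore cancels this scheduled draw for everyone.

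**3. Blood volumes: is plasma counted?**

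Inputs are the SoA rows.

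- *Groups 7 and 9 (stated 140.5 mL).* Screening 8 + Visit 2 (15 + 2.5) + six humoral draws of 10 + two of 15 = 8 + 17.5 + 60 + 30 = 115.5. Adding five plasma draws, 5 × 5 = 25, gives 140.5. Reproduced only with all five.
- *Groups 1-5, PBMC subset (stated 460.5 mL).* 8 + 17.5 + eight draws of 10 + two of 15 = 135.5. Adding 5 × 60 = 300 PBMC gives 435.5, and adding 25 plasma gives 460.5. Reproduced only with all five.
- *Groups 1-5, non-PBMC (stated 155.5 mL).* 135.5 + 25 = 160.5, not reproduced. The stated figure matches four plasma draws, 135.5 + 20. Visit 14 is printed as 15 mL, but its rows give 15 + 5 = 20.
- *PBMC cumulative row.* At Visit 12 it goes from 305.5 to 385.5, a rise of 80 against a daily figure of 75. It should be 380.5. At Visit 14 it then rises 75 against a daily figure of 80, so the errors cancel and the end total is right.
- *Group 6, non-PBMC (stated 258 mL).* SoA 1.3.4 adds 2.5 + 70 humoral + 6 × 5 plasma = 102.5, and 155.5 + 102.5 = 258. From a base of 160.5 it is 263.

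The totals thus count plasma that the footnotes would cancel.

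**4. Groups 9-10, Day 29**

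SoA 1.3.3 marks hematology serum at Day 29, but its humoral row and its volume row are both empty there. No stored serum stands behind that mark. Table 6 in Section 8 nevertheless calls the same visit a safety and immunogenicity visit.

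**The case against.** Much can be said on the other side.

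- **Most of the text points to serum.** The second sentence of 8.2.4, the SoA key and the serum row agree, so the plasma phrase is the outlier. That is fair and supports the direction of the fix, but the phrase is an explicit prohibition in the section that governs the test.
- **The plasma footnote looks like one misprint repeated.** The amendment history also ties plasma collection in all groups to Amendment 3. This is plausible. The instruction still stands in three current schedules.
- **A reader might infer that no plasma is collected for D-dimer and lupus anticoagulant at all.** The documents do not support this. SoA 1.3.4 schedules 5 mL plasma at Visits 101, 102, 103, 105, 106 and 107 without the Amendment 2 limit, for the open-label recipients in Groups 6, 8 and 10 (target 75). Serum is marked at the same visits, so anti-PF4 before and after their first active dose is also covered.
- **A reader might infer that suspected TTS could not be investigated.** That does not follow either. Section 8.3.6.1 calls for local anti-PF4 testing after any thrombotic event or thrombocytopenia, and Appendix 2 allows testing of the stored pre-vaccination sample. The conflict concerns routine exploratory testing only.
- **New wording cannot recover missed plasma.** The Amendment 6 summary of changes says that all adults had received Injection 3 before Amendment 4 was implemented, so plasma at Visits 6 to 9 is past. In SoA 1.3.1 only the 12-month draw can still be settled. Stored serum can still be tested.

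**Conclusion.** The contradiction is real and lies in current text. It is limited to the blinded adult regimens in SoA 1.3.1 to 1.3.3 set against Section 8.2.4.

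Its consequence is that baseline and post-dose-1 anti-PF4 may be missing for participants whose early visits predate Amendment 2. It would be wrong to say that 400 participants lose their baseline: 400 is the planned size of Groups 1-6 and only an upper bound. The overcounting of emerging abnormalities assumes that anti-PF4 enters the SAP 5.6.2 laboratory tables, where it would be judged against normal ranges because SAP Appendix 3 has no grade for it.

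The endpoints are exploratory and descriptive, so no primary or secondary result changes. What suffers is the ability to read coagulation results against a pre-vaccination value. The point should be corrected, because the remedy is cheap and the serum is already stored. The volume errors are 5 mL each and matter mainly as evidence that rows, footnotes and totals were not updated together.

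**What to change.** 1. In 8.2.4, delete anti-PF4 from the sentence that rules out retrospective testing. State that it is run on stored humoral serum at every visit where humoral serum was drawn, including Day 1.
2. Make footnote v of SoA 1.3.1, footnote u of 1.3.2 and 1.3.3, and Section 8.2.4 give one plasma collection period.
3. Give one start for hematology serum, Amendment 3 or Amendment 4/5, in both places.
4. Resolve the Groups 9-10 Day 29 serum mark, which has no humoral draw behind it.
5. Correct the PBMC cumulative volume at Visit 12 from 385.5 to 380.5 mL in either case. If the 12-month plasma draw is kept, change the non-PBMC Visit 14 volume from 15 to 20 mL, so that 155.5 becomes 160.5 and the Group 6 figure of 258 becomes 263. If it is dropped, remove it from all rows and totals: 460.5 − 5 = 455.5 and 140.5 − 5 = 135.5, with the Group 6, 8 and 10 totals following.

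A small table listing each test with its matrix, visits, start and stop amendment, and whether it is run retrospectively would settle items 1 to 4 together.

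The cost is a wording amendment plus the assay runs. Item 1 needs no extra draw, because it is limited to visits where humoral serum was taken.
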